1.4 Justification for the Investigation

In order to study the safety and effectiveness of the *Esteem® System* in a clinical environment, a post-approval study was requested by FDA. This post-approval study will include a minimum of 45 subjects implanted by newly-trained surgeons at 5 to ten investigational sites followed through their 1-year follow-up visit for both safety and efficacy endpoints. In addition, an extension of the PMA pivotal clinical trial conducted under IDE G070162 was conducted as a separate post-approval study. That study demonstrated long-term safety and effectiveness through 5-year follow-up.

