1.5 Duration of the Investigation

The post-approval study will commence immediately upon PAS Protocol approval. Subjects will be followed at 1, 4 and 10-months post-activation and annually thereafter through 1 year.

2 STUDY DESIGN AND OVERVIEW**2.1 Trial Design**

This Post Approval Study is designed as a prospective, multi-center, non-randomized, clinical trial to evaluate the safety and efficacy of the *Esteem® System* implanted by newly-trained surgeons. For this trial the subject will act as his or her own control.

This trial has been designed to meet United States' regulatory requirements.

Each subject will act as both the test subject and the control by being tested prior to implant in both the unaided and aided condition.

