4.5.3 Follow-up Visits

The subjects will return to the clinic for follow-up visits after the device is activated. The visits will occur at 1 month (± 3 weeks), 4 months (± 3 weeks) and 10 months (±3 weeks) post activation. The visits will consist of the testing outlined in Table 1.

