4.7 Adverse Events

The 109 subjects to be reported for the Adverse Event endpoint will consist of the 45 newly-implanted subjects supplemented by data from a retrospective chart review of "commercial" (non-study subjects).

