4.7.1 Definitions

Adverse Event (AE): An Adverse Event is any undesirable clinical event occurring to a subject, during a clinical trial, whether or not it is considered related to the investigational product. This includes a change in a subject's condition or laboratory results, which has or could have a deleterious effect on the subject's health or well-being, including failure of bone conduction/safety algorithm.

Serious Adverse Event (SAE): A Serious Adverse Event (SAE) or a Serious Adverse Device Effect (SADE) are events which:

- Results in death
- Is life threatening
- Results in persistent or significant disability / incapacity
- Results in a congenital anomaly / birth defect
- Requires or prolongs in-patient hospitalization (>24 hours)
- Requires intervention to prevent permanent impairment/damage

Unanticipated Adverse Device Effect (UADE): An Unanticipated Adverse Device Effect is any serious adverse effect on health or safety or any life-threatening problem or death caused by, or associated with, a device, if that effect, problem, or death was not previously identified in nature, severity, or degree of incidence in the investigational plan or application (including a supplementary plan or application), or any other unanticipated serious problem associated with a device that relates to the rights, safety, or welfare of subjects. NOTE: an UADE is, by definition, serious in nature.

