4.7.2 Reporting of Adverse Events

The procedure for reporting any AE is as follows:

- All Adverse events will be documented on an Adverse Event Form
- The Investigator is responsible for reporting AEs to his or her IRB in accordance to their site's IRB procedures.
- The Investigator shall report all unanticipated adverse device effect to the Monitor/Sponsor as soon as possible, but definitely no later than 10 days after obtaining knowledge of event.
- The Sponsor is responsible for informing the FDA, all reviewing IRBs and other investigators of any unanticipated adverse device effect that has occurred.

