5 STATISTICAL ANALYSIS

5.1 Sample Size

For the effectiveness objectives, based upon the following analysis and 0204 clinical data, a sample size of 45 new subjects meets the guidelines for statistical power. For the facial pareses/paralysis objective with an end point of 1 month, a sample size of 109 subjects is required as shown below.

SRT

Based on a mean improvement in SRT over hearing aid of 10 dB and a standard deviation of 13 dB, 45 subjects at 1 year would provide at least 80% power for testing non-inferiority and superiority at a one-sided 0.05 alpha level. A margin of – 5 dB will be used for non-inferiority and a margin of +5 dB will be used for superiority.

WRS

Based on a mean improvement in WRS over hearing aid of 22% and a standard deviation of 31, 45 subjects at 1 year would provide at least 80% power for testing non-inferiority and superiority at a one-sided 0.05 alpha level. A margin of –10% will be used for non-inferiority and a margin of +10% will be used for superiority.

Facial Pareses/paralysis:

Based upon a null hypothesis of 7% and a hypothesized true rate of 2% of facial paresis/paralysis, 109 subjects at 1 month would provide at least 80% power for testing the hypothesis.

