Additional Analyses: The Word Recognition Scores will be compared using the Thornton and Raffin (1978) published upper and lower limits for various word lists based upon percentage scores. Based upon this, an analysis of the % better than, % equal to and % below the aided condition (HA) will be presented.

Reference:

Objective 3: To determine the incidence rate of Serious Adverse Device Effects (SADE) and the incidence rate of device failures and replacements.

Endpoint: The analysis of the incidence of SADEs and device failures and replacements at each follow-up.

Hypotheses: There is no formal hypothesis. This objective is to provide an accurate estimate of the SADE rate and device failure and replacement rate associated with the *Esteem® System*.

Statistical Analyses: The incidence of SADEs and device failures and replacements will be estimated with the observed number of SADEs and device failures and replacements over the total person-months of follow-up at each follow-up. The upper bound of the one-sided 95% exact binomial confidence interval on the SADE rate and device failure and replacement rate will be calculated and reported.

Objective 4: To demonstrate that the incidence of facial pareses/paralysis is no greater than the 7% incidence experienced in the PMA clinical trial.

Endpoint: The analysis of the incidence of facial pareses/paralysis at 1 month follow-up.

Criterion for success: The 95% Upper Confidence Bound (UCB) for the incidence of facial paresis/paralysis ($p_{\text{paresis/paralysis}}$) is less than 7%

$$95\% \text{ UCB for } p_{\text{paresis/paralysis}} < 7\%$$

Statistical Analyses: The upper bound of the one-sided 95% exact binomial confidence interval on the incidence of facial paresis/paralysis will be compared to 7% and success declared if it is lower than 7%.

Objective 5: To demonstrate that the subject's cochlear function remains unchanged with the *Esteem®* system as shown by comparison of the subject's pre-implant baseline Bone Conduction Threshold (BCT) vs. the subject's post activation BCT.

Endpoint Analysis: Bone conduction will be measured with forehead probe placement. The Safety Algorithm as described in Attachment C, will be used for any Bone Conduction results outside the stability range.

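### Does pooling 45 trial subjects with chart-review subjects leave Objective 4 without a usable counting rule?

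*Combined protocol and SAP*

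**What the plan says.** Section 5.2 (Objective 4) sets the endpoint as "Endpoint: The analysis of the incidence of facial pareses/paralysis at 1 month follow-up". Success requires the one-sided 95% exact binomial upper bound to be below 7%.

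Section 5.1 takes a null rate of 7% and a true rate of 2%, and states that "109 subjects at 1 month would provide at least 80% power for testing the hypothesis".

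Sections 2.2 and 4.7 say where the 109 come from. Section 4.7 states: "The 109 subjects to be reported for the Adverse Event endpoint will consist of the 45 newly-implanted subjects", and the same sentence adds a retrospective chart review of commercial, non-study patients. The Protocol Summary makes 109 a minimum number of evaluable subjects for safety.

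Section 4.7.1 defines an adverse event as "any undesirable clinical event occurring to a subject, during a clinical trial", and section 4.7.2 says "All Adverse events will be documented on an Adverse Event Form".

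On timing, section 4.5.3 says "The visits will occur at 1 month (± 3 weeks), 4 months (± 3 weeks) and 10 months (±3 weeks) post activation", and section 4.5.2 puts activation at 8 ± 2 weeks after implant. Section 1.5 says "Subjects will be followed at 1, 4 and 10-months post-activation and annually thereafter through 1 year", while section 1.4 has subjects "followed through their 1-year follow-up visit for both safety and efficacy endpoints".

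**The concern.** A single binomial proportion assumes that the same event is counted in the same way in everyone in the denominator. Here up to 64 of the 109 (59%) come from records that were not kept under the protocol. Two features of the text suggest that the charts fall outside its rules.

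- **Definition.** Read literally, the adverse-event definition covers only what happens in a clinical trial and is recorded on a trial form. A commercial patient's facial paresis is neither.
- **Clock.** The 1, 4 and 10 month visits run from activation, yet the 1-year label has no visit of its own and fits only if time is counted from implant. A chart abstractor might then take 1 month to mean one month after surgery.

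The plan also does not say, for the charts, whether a case is counted by onset or by status at the visit, whether a transient palsy counts, how charts are chosen, or what happens when a chart is silent. Section 3.2 lists facial paralysis as a risk of the operation, so early cases are plausible. A missed chart case can only make the test easier to pass. At stake is the one primary safety objective that has a formal pass criterion.

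**Working it through.** **Inputs.** Null rate 7%, assumed true rate 2% and n = 109 (section 5.1); one-sided 95% exact bound (section 5.2); 45 trial subjects (sections 2.2 and 4.7). Charts at the stated minima: 109 − 45 = 64.

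**1. Reproduce the plan's figure.** The exact upper bound for x cases in n is the 0.95 quantile of Beta(x + 1, n − x).

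- 3/109: 6.96%, pass.
- 4/109: 8.20%, fail.

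The rule is therefore to pass with at most 3 cases.

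- Type I error: P(X ≤ 3 | 109, 0.07) = 4.85%.
- Power: P(X ≤ 3 | 109, 0.02) = 82.5%.

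The stated 80% is met, and 109 is the smallest n that meets it under this rule.

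**2. What incomplete chart counting would do.** Let f be the share of chart cases not counted (an assumption; no document gives a value). At a true 7% in both sources, X1 ~ Bin(45, 0.07), X2 ~ Bin(64, 0.07(1 − f)), and the test passes if X1 + X2 ≤ 3. Expected cases at f = 0 are 45 × 0.07 = 3.15 and 64 × 0.07 = 4.48, total 7.63.

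| f | P(pass at a true 7%) |
|---|---|
| 0 | 4.85% |
| 10% | 6.6% |
| 22.7% (about one of 4.48) | 9.7% |
| 25% | 10.4% |
| 50% | 20.6% |
| 100% | 61.3% |

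The last row keeps 64 people in the denominator who can never contribute a case. That defeats the stated purpose of adding them, so it is an arithmetic limit and not a reading of the plan.

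**3. When one missed case matters.** It changes the verdict only if the full count is exactly 4. P(X = 4 | n = 109) is 10.7% at a true 2% and 6.6% at a true 7%.

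**4. Evaluability.** At n = 108 the limit falls to 2 cases (3/108 gives 7.02%) and power at 2% is 63.3%. The Protocol Summary's minimum of 109 evaluable subjects already rules this out.

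**5. The definition.** The statement that commercial patients belong to the adverse-event endpoint opens section 4.7; the definition and the reporting form are its subsections. The specific statement governs, and the trial wording in 4.7.1 is stock language. Objective 4 also does not work through that definition: it names facial paresis or paralysis directly.

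**6. The clock.** With 1 month = 4.35 weeks, the 1-month visit falls nominally 8 + 4.35 = 12.3 weeks after implant, with range 6 + 4.35 − 3 = 7.3 to 10 + 4.35 + 3 = 17.3 weeks. The 10-month visit falls at 8 + 43.48 = 51.5 weeks, which explains the loose 1-year label. Sections 1.5 and 4.5.3 both put the 1-month visit after activation, and nothing defines a 1-month visit from implant. The 1-year label plays no part in Objective 4. If cases are counted cumulatively from surgery, early operative cases are included on either clock.

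**The case for a change.** The strongest case for a change is that the chart review has one sentence in each of two sections, while charts supply up to 59% of the denominator of a test that turns on a single case. Section 4.2, which keeps safety data through the 1-month follow-up, and section 4.4, which has clinical events recorded before discharge, support a cumulative count, but only for trial subjects. Even if every reader agrees that chart cases count, the date from which they count and the handling of a silent chart remain open. One short definition covering both sources would cost little and need no extra visits.

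Much of this stands as description. The abstraction rule is not written down, and a retrospective record holds only what someone noted. It does not show that the planned test is wrong. Incidence of an operative complication is naturally read as any case from surgery up to the follow-up point, and the same reading can be applied to a chart. The inflation figures depend on a loss share that the documents do not give. Showing counts by source would be informative, but it would not alter the pass criterion. A fixed order for taking charts answers a selection problem for which the text offers no evidence beyond silence. Nor do the documents say how the 7% from the PMA trial was counted, so no direction of bias against that figure can be established.

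**Conclusion.** The concern does not call for a change. The apparent conflicts over definition and clock disappear when section 4.7 is read with its subsections and the 1-month visit is taken from sections 1.5 and 4.5.3. What is left is missing abstraction detail that analysts would ordinarily settle in the chart-review procedure: count every facial paresis or paralysis from surgery through the 1-month follow-up, by the same rule in both sources. On that basis the design performs as stated, with at most 3 cases in 109, type I error 4.85% and power 82.5% at a true 2%.

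This conclusion assumes that chart cases are captured essentially completely. If 10% were missed, the chance of passing at a true 7% would be 6.6%; at 22.7% missed it would be 9.7%. Both use the 45 + 64 split, which follows from two stated minima. Subjects whose hearing aid fails the real-ear check can count for safety but not for efficacy (section 4.2), so there may be more trial subjects and fewer charts, and the effect of any chart loss would then be smaller.

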2. To demonstrate that the *Esteem® System* is as effective as or better than the hearing aid for improving speech discrimination (intelligibility) as shown by the word recognition score at 50 dB.

Endpoint: Comparison of the word recognition score using the *Esteem®* compared to the pre-implant aided condition.

3. To determine the incidence of Serious Adverse Device Effects (SADE) and Adverse Device Effects (ADE) and the incidence rate of device failures and replacements.

Endpoint: The analysis of the incidence of SADEs and device failures and replacements at each follow-up.

4. To demonstrate that the incidence of facial pareses/paralysis is no greater than the 7% incidence experienced in the PMA clinical trial.

Endpoint: The analysis of the incidence of facial pareses/paralysis at 1 month follow-up.

5. To demonstrate that the subjects' cochlear function remains unchanged with the *Esteem® System* as shown by comparison of the subjects' pre-implant baseline bone conduction threshold versus the subjects' post-activation visit bone conduction threshold.

Endpoint: Comparison of bone conduction threshold (BC) using forehead placement post activation compared to the pre-implant BC threshold.

Secondary Objectives:

1. To show that the *Esteem® System* improves Quality-of-Life when compared to the baseline aided condition as shown by APHAB results.
2. To gather subject feedback and comments on the use of the *Esteem® System* relative to the pre-implant hearing aid (aided condition) as shown by the *Esteem® Questionnaire*.

Sponsor Contact Information:

Envoy Medical Corporation, Inc. (EMC)

[name]

[name]

[contact]

Customer Service [contact]

www.envoymedical.com

Changes in Revision 04

Change footer revision number from Rev 03 to Rev 04
Clarify the enrollment totals for efficacy and safety endpoints in Protocol Summary, sections 1.4, 2.2 and 4.7
Change sponsor address of Envoy Medical Corporation to current address
Miscellaneous typo corrections

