2.2 Investigational Sites and Number of Enrollments

The post-approval study will enroll a minimum of 45 new subjects on a consecutive consenting basis at 5 to 10 investigational sites to be implanted by newly-trained surgeons. These subjects will be evaluated for both efficacy and safety endpoints. The goal will be to monitor the subjects through their one (1) year follow-up. NOTE: In order to achieve the required sample size of 109 subjects for the safety endpoints, data from these 45 new subjects will be supplemented by data from a retrospective chart review of "commercial" (non-study subjects).

Trial Objectives

The overall objective of the study is to evaluate the safety and effectiveness of the *Esteem® System* implanted by newly-trained surgeons in subjects suffering from moderate to severe hearing loss.

Primary Objectives:

- 1) To demonstrate that the *Esteem® System* improves the speech threshold of sensitivity for hearing and identifying speech signals as well as or better than the pre-implant hearing aid (aided condition).
Endpoint: Comparison of the speech reception threshold (SRT) using the *Esteem® System* as compared to the pre-implant aided condition.
- 2) To demonstrate that the *Esteem® System* is as effective as or better than the hearing aid for improving speech discrimination (intelligibility) as shown by the word recognition score at 50 dB.
Endpoint: Comparison of word recognition score using the *Esteem®* as compared to the pre-implant aided condition.
- 3) To determine the incidence of Serious Adverse Device Effects (SADE) and Adverse Device Effects (ADE) and the incidence rate of device failures and replacements.
Endpoint: The analysis of the incidence of SADEs and device failures and replacements at each follow-up.
- 4) To demonstrate that the incidence of facial pareses/paralysis is no greater than the 7% incidence experienced in the PMA clinical trial.
Endpoint: The analysis of the incidence of facial pareses/paralysis at 1 month follow-up.
- 5) To demonstrate that the subjects' cochlear function remains unchanged with the *Esteem® System* as shown by comparison of the subjects' pre-implant baseline bone conduction threshold versus the subjects' post-activation visit bone conduction threshold.
Endpoint: Comparison of the bone conduction threshold with forehead placement compared to the pre-implant bone conduction threshold.

Secondary Objectives:

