ATTACHMENT A: *Safety Algorithm*

Bone Conduction/Safety Algorithm

Introduction

Bone conduction (BC) using forehead probe placement will be the primary test for cochlear function stability. While forehead placement will minimize some of the test variability issues associated with the mastoid probe placement as detailed in IDE G000321, there remains the possibility that BC test-retest variability may result in test results outside the ± 10 dB limits due to equipment limitations and probe placement. As an improvement over the methods used in IDE G000321, the Safety Algorithm has been refined for use in this new clinical trial. In addition to bone conduction, the EnvoyGram function will be used as an in-situ audiogram to directly stimulate the cochlea. This method will be more accurate and a better indicator of cochlear stability than the previous EnvoyGram tests where testing done at implant was used to predict future performance.

The EnvoyGram IT

In addition to the programmable parameters used to affect the incoming signal, the Sound Processor has an internal tone generator that can be accessed through the *Esteem®* Programmer in a test mode called the EnvoyGram IT (EnvoyGram In-situ).

Simply put, the EnvoyGram IT is an in-situ audiogram utilizing the Driver to test cochlear function. When entering this test mode, the Sensor is deactivated. The *Esteem®* Programmer software allows the audiologists to select a frequency in the range 250 to 4000 Hz and amplitude in the range 55 to 119 dB SPL. The Sound Processor synthesizes and delivers a pure tone signal to the Driver to induce known vibrations directly into the cochlea. There are twelve steps of amplitude. Each step provides a 4 - 6 dB increase over the previous step. The typical EnvoyGram IT levels are based on:

- a. a typical intact chain displacement of 40 nm at 100 dB for frequencies below 1 kHz (Validated per ASTM F 2504 and EMC 003798-001),
- b. a typical Model 7502 Driver displacement in temporal bones of 88 nm/V (Validated per EMC 003798-001), and
- c. a typical SP tone output for each volume and tone setting (Validated per EMC 003788-101 and EMC 003872-001).

Each patient's intact chain has a unique displacement profile. During implant of the *Esteem®*, intact chain data is measured and recorded to provide a normalization factor for the EnvoyGram IT.

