Since the EnvoyGram IT levels are calibrated to each patient, the "predicted" EnvoyGram IT thresholds are equal to the baseline pre-implant unaided audiogram for each test frequency. For instance, a patient with 55 dB baseline air conduction threshold at 1 kHz and 80 nm measured IC would have a predicted EnvoyGram IT of 58 dB at 1 kHz (first level above baseline unaided threshold of 55 dB).

Bone Conduction/Safety Algorithm

Safety Algorithm Explanation:

The first level of the safety algorithm will use standard bone conduction (BC) thresholds. Bone conduction thresholds are measured in the implanted ear at 0.5, 1.0, 2.0, and 4.0 kHz at baseline and follow-up visits. If less than two (2) of the follow-up thresholds are more than 10 dB greater than the baseline thresholds, then the individual test frequencies are evaluated. At each test frequency, if the follow-up threshold is less than 20 dB greater than the baseline threshold then the algorithm is considered complete, with a conclusion that no change cochlear function occurred. However, if at least two (2) of the thresholds have increased more than 10 dB or if any individual threshold has increased by 20 dB or more, then the EnvoyGram data is evaluated.

The second level of the safety algorithm will use EnvoyGram thresholds. Baseline unaided air conduction pure tone thresholds at 0.5, 1.0, 2.0, and 4.0 kHz are measured at baseline. Similarly, EnvoyGram thresholds are measured in the implanted ear at 0.5, 1.0, 2.0, and 4.0 kHz at follow-up visits. Based on the intra-operative intact chain data, an EnvoyGram equivalent dB threshold is calculated for each of the four test frequencies. If less than two (2) of the follow-up EnvoyGram thresholds are more than 10 dB greater than the baseline thresholds, then the individual test frequencies are evaluated. At each test frequency, if the follow-up EnvoyGram threshold is less than 20 dB greater than the baseline threshold

then the algorithm is considered complete, with a conclusion that no change in cochlear function occurred. However, if at least two (2) of the EnvoyGram thresholds have increased more than 10 dB or if any individual EnvoyGram threshold has increased by 20 dB or more, then the algorithm is considered complete with a conclusion that a change in cochlear function occurred.

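### Primary Objective 5 sets out to demonstrate unchanged cochlear function but has no group estimate, confidence bound, decision rule or deciding visit

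*Combined protocol and SAP*

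**What the plan says.** Section 5.2 opens Objective 5 with "To demonstrate that the subject's cochlear function remains unchanged with the" device. The Protocol Summary and the objectives list under section 2.2 both make it a primary objective. The Protocol Summary gives the endpoint as "Comparison of bone conduction threshold (BC) using forehead placement post activation compared to the pre-implant BC threshold". The section 2.2 list gives it as "Comparison of the bone conduction threshold with forehead placement compared to the pre-implant bone conduction threshold". Neither names a statistic, and the visit is no more specific than post activation.

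The analysis text in 5.2 has two sentences. One fixes forehead probe placement. The other reads "The Safety Algorithm as described in Attachment C, will be used for any Bone Conduction results outside the stability range". The stability range is not defined there; the only matching figure is in the introduction to Attachment A, which warns of "test results outside the ± 10 dB limits due to equipment limitations and probe placement".

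Attachment A sets out the algorithm for 0.5, 1, 2 and 4 kHz in the implanted ear. Level 1 uses bone conduction (BC): "If less than two (2) of the follow-up thresholds are more than 10 dB greater than the baseline thresholds", each frequency is looked at on its own, and if each shift is below 20 dB, "then the algorithm is considered complete, with a conclusion that no change cochlear function occurred". Otherwise the ear goes to Level 2, which applies the same cut-offs to EnvoyGram thresholds and makes the final call. A closing paragraph covers non-responses. A frequency with a baseline non-response is not evaluated, and a new non-response at follow-up is replaced by the EnvoyGram threshold.

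Section 4.7.1 counts failure of the algorithm as an adverse event. Table 1 of section 4.6 schedules BC at baseline, activation, and 1, 4 and 10 months.

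**The concern.** The other primary objectives show what is missing. Objectives 1, 2 and 4 each have a 95% confidence-bound criterion. Objective 3 says that it tests no hypothesis and still reports an upper bound. Objective 5 claims to demonstrate something, yet has neither a criterion nor such a disclaimer, and section 5.1 gives it no sample-size statement.

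Cochlear damage is a listed risk in section 3.2, so this is a substantive safety question. Under the current text, two analysts with the same data could reach opposite conclusions on the objective and both be following the plan. They could also choose different visits. A per-ear classification is a weak instrument for a small loss shared by most ears, and that is the kind of change a group estimate would show.

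**Working it through.** **Is there a figure to reproduce?** No. The documents give no sample size, power, margin or rate for Objective 5. The neighbouring objectives do reproduce. For SRT superiority, (10 − 5)/(13/√45) = 2.580; 2.580 − 1.645 = 0.935; Φ(0.935) = 82.5%. For facial paresis with 109 subjects, up to 3 events pass (exact upper bound 6.96%), with power 82.5%. Both agree with the stated minimum of 80%, so the gap is particular to Objective 5.

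**Level 1 rule, from Attachment A.** An ear goes on to Level 2 if at least two of four shifts exceed 10 dB, or any shift is 20 dB or more.

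- Shifts 10/10/10/10: none exceeds 10 dB and none reaches 20 dB, so no change.
- Shifts 15/10/10/10: one exceeds 10 dB and none reaches 20 dB, so no change. The mean loss is 45/4 = 11.25 dB.
- Shifts 15/15/0/0: two exceed 10 dB, so Level 2.

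**Level 1 with measurement noise.** Assumptions, none of them in the documents: true loss m at every frequency, normal error in the change with SD s of 3 to 7 dB, independent across frequencies, change recorded to the nearest 5 dB. Let q be the chance that a recorded shift is 10 dB or less, and p the chance that it is exactly 15 dB:

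q = Φ((12.5 − m)/s), p = Φ((17.5 − m)/s) − q, P(flag) = 1 − q⁴ − 4pq³

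| m (dB) | s (dB) | q | p | q⁴ | 4pq³ | Flagged |
|---|---|---|---|---|---|---|
| 5 | 3 | 0.9938 | 0.0062 | 0.9754 | 0.0243 | 0.03% |
| 5 | 5 | 0.9332 | 0.0606 | 0.7584 | 0.1970 | 4.5% |
| 5 | 7 | 0.8580 | 0.1049 | 0.5420 | 0.2651 | 19.3% |
| 10 | 3 | 0.7977 | 0.1961 | 0.4049 | 0.3982 | 19.7% |
| 10 | 5 | 0.6915 | 0.2417 | 0.2286 | 0.3197 | 45.2% |
| 10 | 7 | 0.6395 | 0.2185 | 0.1673 | 0.2286 | 60.4% |

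A uniform 10 dB loss would thus send about 9 to 27 of 45 ears to Level 2 (45 × 0.197 and 45 × 0.604). Level 2 is not modelled, so these are not final classifications.

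**What 45 ears could support.**

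- Proportion changed, one-sided exact 95% upper bound: 0 of 45 gives 1 − 0.05^(1/45) = 6.4%; 1 of 45 gives 10.1%; 2 of 45 gives 13.3%.
- Paired mean change: the bound lies t(0.95, 44) × SD/√45 from the mean, with t = 1.680. The SD of BC change is not in the documents. At an assumed 4 dB the distance is 1.680 × 4/6.708 = 1.0 dB; at 10 dB it is 2.5 dB; at 13 dB it is 3.3 dB. This takes all 45 ears as complete.

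**The case against.** The strongest defence is that the plan does contain a working test. The algorithm can conclude that cochlear function changed in an ear, and a failure is then an adverse event. The 10 dB allowance is there because BC testing varies between sessions. This stands as a reason for a wide limit on a single ear. It is no reason to omit a group estimate, since random error averages out over 45 ears and a shared loss does not. Nor does the adverse-event route tie any count of ears to Objective 5.

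The defence does rule out several stronger readings that a reader might infer:

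- *The objective cannot fail.* Without a rule it can formally neither fail nor succeed, and single ears can be classed as changed.
- *A 10 dB loss across the group would be reported as no change.* Having 0 of 45 ears flagged needs a shift of exactly 10 dB and no measurement error. With the assumed error, 20% to 60% of ears are flagged at Level 1.
- *The algorithm replaces the threshold comparison and the measurements are discarded.* Section 5.2 applies it to results outside the stability range. The comparison itself is left unspecified; it is not excluded.
- *The 5 dB SRT margin shows that 10 dB is too lax.* The SRT margin concerns a group mean difference in aided speech threshold. The 10 dB limit concerns one ear at one frequency. They are not like for like.

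A mean BC analysis also has a difficulty of its own: Attachment A expects non-responses in this population, and an average is undefined for such ears until a rule is written.

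**Conclusion.** The concern holds as a missing decision rule for a primary safety objective. That part rests on the text alone: no group statistic, bound, pass value or deciding visit appears anywhere, so following the plan exactly yields no conclusion on Objective 5.

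The secondary finding is that Level 1 is insensitive to a modest shared loss, flagging about 0% to 19% of ears at a uniform 5 dB. It is not blind to 10 dB. These rates depend on the assumed SD, the 5 dB step and independence across frequencies, and cover Level 1 only. The statement that exactly 10 dB at all four frequencies is classed as no change needs none of those assumptions, only the literal wording.

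**What to change.** In section 5.2, Objective 5:

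1. Keep the Safety Algorithm as the per-subject endpoint. Name the deciding visit, for example 10 months. Report the number changed over the number evaluable with the one-sided exact 95% upper bound.
2. Add the paired mean BC change from baseline over 0.5 to 4 kHz in the implanted ear, with a one-sided 95% upper bound. State the non-response rule in advance and keep it consistent with Attachment A: leave out frequencies with a baseline non-response, and do not simply drop new non-responses at follow-up, because they may be the worst outcomes and dropping them could bias the mean towards no loss.
3. Either set a pass value before analysis and justify it on BC grounds (the SRT margin is not a justification), or change the wording from demonstrating to estimating and report the bounds, on the model of Objective 3.
4. Define the stability range in 5.2 and correct the attachment reference: the text cites Attachment C, but the algorithm is in Attachment A.

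The cost is revised analysis wording, a non-response rule and one further paired analysis. No visit or test is added, since Table 1 already schedules the measurements. The safety statement may read less favourably.
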